### 7.7.2 Clinical Laboratory Evaluation

Descriptive statistics for test results and change from baseline (Visit 2/Day 0 from protocol 093-045 or 093-046) will be displayed at each scheduled visit (i.e. Visit 3-Visit 7) for each continuous laboratory parameter.

The normal reference ranges for laboratory tests will be used to determine whether the laboratory test value is below, within, or above the normal range. Shifts from baseline to each visit will be produced to show the percentage of subjects with laboratory test values below, within, and above the normal range. The percentage will be based on the number of subjects with a baseline result and at least one post-baseline result for each parameter.

Clinical significance of post-baseline abnormally low and high values will be summarized for each lab parameters.

A listing of urine drug screen and serum pregnancy test results will also be provided.

For laboratory parameters with categorical outcomes, the number and percentage of subjects with each outcome will be presented.

The number and percentage of subjects with PCS criteria will be summarized by overall, and by the subgroups including age group, race, gender, number of baseline AED and baseline AEDs.

The listing of the Special Interest of Elevation defined as elevation of any post-dose AST or ALT > 3x ULN will be provided.

Listing of clinical laboratory measurements (hematology, serum chemistry, urinalysis, blood coagulation, bone turnover marker measurements) will be provided.

In addition, listing of clinically significant out of range laboratory measurements, laboratory comments, and listing of subjects meeting any of the PCS lab criteria will be provided.

In addition to continuous summaries of blood sodium levels, the number and percentage of subjects with normal baseline sodium level and a post-baseline level  $\leq 135$  mEq /L but  $> 130$  mEq /L,  $\leq 130$  mEq /L but  $> 125$  mEq /L,  $\leq 125$  mEq /L, and  $> 10$  mEq/L reduction (i.e.  $< -10$  mEq/L) from baseline will be summarized by time point and overall post-baseline.

Above blood sodium levels will be also summarized by baseline AED and for actual monotherapy used subgroup.

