## 5. Efficacy and Safety Variables

### 5.1. Schedule of Evaluations

Procedures	Visit 1/ SCN a	Visit 2	Visit 3	Visit 4	Visits 5 and 6	Visit 7	Post-1-year Visit 8 onwards	EOS/ET	Computer Systems c
	Day 0	Week 1	Mont h 1	Mont h 3	Months 6 and 9	Month 12	Month 15 onwards b		
Informed Consent	X								
Inclusion/Exclusion Criteria Review	X								A
Physical Examination	• d							X	A
Neurological Examination	•							X	A
Vital Sign Measurements	•	X	X	X	X	X	X	X	A
Height	•							X	A
Weight e	•	X	X	X	X	X	X	X	A
Clinical Laboratory Evaluation (Serum Chemistry, Hematology, and Urinalysis) f	•		X	X	X	X		X g,h	B
Coagulation Testing (PT/INR, PTT)	•		X	X	X	X		X g	B
Thyroid Panel (T 3 , T 4 , and TSH)	•		X	X	X	X		X g	B
Lipid Panel (total cholesterol, HDL-cholesterol, LDL-cholesterol, and triglycerides) f	•		X	X	X	X		X g,h	B
Bone Turnover Markers i	•				X h	X		X g	B
Serum Pregnancy Test k	•		X	X	X	X		X g	B
Urine Pregnancy Test k							X	X	
Urine Drug Screen (Central Lab)	•								B
12-Lead ECG	•		X	X	X	X		X h	C
MADRS	•				X j	X	X l	X	A
QOLIE-31 m	•				X j	X	X il	X	A
PGI Scale							X	X n	
C-SSRS o	•	X	X	X	X	X	X	X	A
Health Outcomes Assessments	•	X	X	X	X	X	X	X	A
Adverse Events	•	X	X	X	X	X	X	X	A
Concomitant Medications	•	X	X	X	X	X	X	X	A
Dispense Seizure Diary	X	X	X	X	X				
Document Seizures in Seizure Diary		X	X	X	X				A
Seizure Diary Review		X	X	X	X	X		X g	

Author:

Version Date: 19May2017

Copyright © 2010 Quintiles Transnational Corp. All rights reserved.

The contents of this document are confidential and proprietary to Quintiles Transnational Corp. Unauthorized use, disclosure or reproduction is strictly prohibited.

Procedures	Visit 1/ SCN a	Visit 2	Visit 3	Visit 4	Visits 5 and 6	Visit 7	Post-1-year Visit 8 onwards	EOS/ET	Computer Systems c
	Day 0	Week 1	Month 1	Month 3	Months 6 and 9	Month 12	Month 15 onwards b		
Dispense Study Drug	X	X	X	X	X	X p	X		A
Dispense Emergency Medication	X								
Drug Accountability		X	X	X	X	X	X	X	A
Dispense/Review MEC	X	X	X	X	X	X	X	X	

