Abbreviations: A=Electronic Data Capture (Inform); B=Laboratory Information Management System (LIMS); C=Core Lab Over-Read; C-SSRS=Columbia Suicidality Severity Rating Scale; EOS=End of Study; ET=Early Termination; MADRS=Montgomery-Asberg Depression Rating Scale; NTx=N-telopeptides of type I collagen cross-links; SCN=Screening; 25-OHD=25-hydroxyvitamin D; TSH=thyroid stimulating hormone; PGI=Patient Global Impression; PTH=parathyroid hormone; QOLIE-31=31-Item Quality of Life in Epilepsy.

- a. Demographic information, medical history, psychiatric history, medication history, magnetic resonance imaging/computerized tomography scans, electroencephalogram data, HLA-B\*1502 genotyping, and Hepatitis B/C screen results collected during the screening visit of Protocols 093-045 or 093-046 will apply for this study as well.
- b. Clinic visits to occur at intervals of 3 months during the post-1-year part.
- c. Letters in this column identify the computerized systems that will be used in this protocol (Appendix IX in protocol).
- d. The symbol “•” represents procedures performed at Visit 9 of Protocols 093-045 or 093-046, the results of which will apply to Visit 1 of the present study as well. These procedures do not have to be repeated.
- e. In street clothes without shoes and jacket/coat.
- f. Fasting labs.
- g. These assessments are not required to be performed if this visit falls in the post-1-year part of the study.
- h. If this visit falls in the post-1-year part of the study, this assessment may be performed only if clinically indicated (per Investigator judgement on a previously noted abnormality).
- i. Includes serum 25-OHD, PTH, osteocalcin, bone-specific alkaline phosphatase, and urinary NTx.
- j. At Visit 5 only.
- k. Every 6 months (i.e. Visits 7, 9, 11, 13, etc.).
- l. Only in subjects ≥18 years at time of signing informed consent in Protocols 093-045 or 093-046.
- m. Only for subjects who discontinue study during the post-1-year part of study.
- n. Fill out “since last visit” scale (Appendix VII in protocol).
- o. Only for subjects who discontinue study during the 1-year part of study.
- p. Only for subjects who continue into the post-1-year part of the study.

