#### Clinical Laboratory Evaluation

Observed values and change from baseline will be summarized for each visit, where change from baseline is the result of interest minus baseline value (Visit 2/Day 0 from protocol 093-045 or 093-046).

Each laboratory result will be cross referenced with laboratory-provided normal reference ranges to determine whether the test result is below, within, or above the normal range. Similarly, sponsor defined-potentially clinically significant (PCS) laboratory results will be identified using the criteria in Table 2.

Additionally, the number and percent of the subjects with normal baseline (Visit 2/Day 0 from protocol 093-045 or 093-046) sodium levels reaching the following post-baseline blood sodium levels as below categories will be identified by time point:

- $\leq 135$  mEq/L and  $> 130$  mEq/L
- $\leq 130$  mEq/L and  $> 125$  mEq/L
- $\leq 125$  mEq/L
- $> 10$  mEq/L reduction (i.e.  $< -10$  mEq/L) from baseline

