### **6.2 Handling of Dropouts or Missing Data**

Subjects who dropped out before study completion are not to be replaced and all available information obtained from them will be included in the appropriate efficacy

and safety summaries to the time of dropout. No imputation is planned for any safety measures.

If the date of the seizure is missing or incomplete and the seizure cannot be allocated to a study interval, these data will not be used in the analysis, but will be presented in the subject data listings. If the seizure diary was returned and there was no seizure data available for a particular day during that evaluation period, it will be assumed that the patient had missing seizure data, and the day will be excluded from the calculation of the standardized seizure frequency.

Seizure related variables will be calculated based on available data. For dropout subjects, their seizure frequency will be derived for each interval up to the last interval where the subject had data. The last interval standardized seizure frequency will be computed based on available data prior to dropout.

For QOLIE31 and MADRS, if only one item is missing, it will be imputed by the average of other items for calculating the total score (See Section 5.2.4: 1 and 2).

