### 7.7.3 ECG Evaluations

Descriptive statistics for each parameter and change from baseline (from protocol 093-045 or 093-046) values will be displayed at each scheduled visit (i.e. Visit 3-Visit 7) for each ECG parameter.

The number and percentage of subjects with QTc-F values in the categories as defined in Section 5.3.2 will be summarized.

- QTc-F >500 ms at any post-baseline time point not present at baseline
- QTcF >480 ms at any post-baseline timepoint not present at baseline
- QTc-F >450 ms at any post-baseline time point not present at baseline
- Change from baseline in QTc-F  $\geq$ 60 ms for at least 1 post-baseline measurement
- Change from baseline in QTc-F  $\geq$ 30 ms for at least 1 post-baseline measurement, but <60 ms for all post-baseline measurements

This categorical analysis will be also performed for QTc-B.

The number and percentage of subjects with ECG abnormalities will be presented in the categories of overall, rhythm, conduction, morphology, myocardial infarction and the presence of ST, T, and U wave abnormalities.

Listing of 12-Lead ECG Measurements, Abnormality Findings and Overall Interpretation, and 12-Lead ECG collections will be provided.

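### SAP 7.7.2 and 7.7.3 give year-1 early-termination values no row in the continuous lab and ECG tables

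*SAP*

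**What the plan says.** On the continuous tables, SAP 7.7.2 says that descriptive statistics for lab results and change from baseline "will be displayed at each scheduled visit (i.e. Visit 3-Visit 7) for each continuous laboratory parameter". SAP 7.7.3 says the same for ECG: "values will be displayed at each scheduled visit (i.e. Visit 3-Visit 7) for each ECG parameter". Neither names the EOS/ET visit.

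The schedule in SAP 5.1 marks serum chemistry, hematology, urinalysis, coagulation, thyroid, lipids, bone markers and the 12-lead ECG in the EOS/ET column. The footnotes relax this only after year 1. Footnote g reads "These assessments are not required to be performed if this visit falls in the post-1-year part of the study", and footnote h allows the assessments it covers, including the ECG, only where clinically indicated.

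Two other places in the SAP are broader:
- The lab endpoint definition in 5.3.2 says "Observed values and change from baseline will be summarized for each visit", and the ECG definition there is worded the same way.
- Section 6.2 says of subjects who drop out that "all available information obtained from them will be included in the appropriate efficacy" and safety summaries, up to the time they leave.

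The lab shift table is described separately in 7.7.2: "Shifts from baseline to each visit will be produced". No range of visits is attached. Its denominator is also stated: "The percentage will be based on the number of subjects with a baseline result and at least one post-baseline result for each parameter".

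**The concern.** The primary objective is long-term safety and tolerability. A subject who stops in year 1 has a final set of labs and a final ECG at the ET visit, and for some subjects these are the only scheduled values under open-label treatment. If the continuous tables stop at the scheduled visits, the mean at each later visit comes from a group that shrinks as subjects leave. If leavers' values differ from stayers', the later means drift towards those who remained. The reader cannot see by how much, because the leavers' last values appear in no continuous summary.

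**Working it through.** The documents give no figure on this point, so the check sets the sections side by side and then sizes the effect on assumed values.

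**1. Are ET values collected in year 1?** Yes. SAP 5.1 marks labs and ECG at EOS/ET, and footnotes g and h waive or restrict them only in the post-1-year part. The gap is therefore mainly a year-1 matter.

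**2. Does any rule place them in a scheduled row?** No.
- The visit windows in 6.1 are defined for seizure data only.
- Section 6.2 plans no imputation for safety measures, so an ET value is not carried to a later visit.
- The range in 7.7.2 and 7.7.3 is introduced by i.e., which defines the set of visits. A programmer following the text would leave ET out.
- Other sections name the ET visit when they intend it: PGI (7.6), orthostatic effects (7.7.5) and C-SSRS (7.7.8).

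**3. Who contributes nothing?** No labs or ECG are scheduled at Visit 2 (Week 1). The first are at Visit 3 (Month 1), and bone markers start at Month 6. A subject who leaves before Month 1 therefore has no value in any continuous lab or ECG row. A subject who leaves before Month 6 has none in the bone-marker rows.

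**4. Which summaries are not limited to Visits 3 to 7?** PCS lab counts; sodium categories, which have an overall post-baseline count; QTc outliers at any post-baseline time point; the summary of clinical significance of abnormal values for each lab parameter; and counts of ECG abnormalities by type.

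**5. What is left uncovered?** The numeric change at ET. Table 2 has no limits for TSH, 25-OHD, PTH, osteocalcin, bone-specific alkaline phosphatase or NTx. PR, QRS and ECG heart rate have no numeric category in 5.3.2 or 7.7.3. A minimum post-dose sodium change is planned, but only for the Actual Monotherapy Used subgroup (6.5).

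**6. Size.** Let p be the proportion who leave before Visit 7, S the mean change in stayers at Visit 7 and L the leavers' mean change at ET. Assume that every stayer has a Visit 7 value and every leaver an ET value.

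Mean including leavers' last values = (1 − p)S + pL

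Visit 7 mean minus that mean = S − [(1 − p)S + pL] = p(S − L)

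With S − L = 2 mEq/L for sodium (assumed):

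| p (assumed) | p × 2 mEq/L |
|---|---|
| 10% | 0.2 |
| 30% | 0.6 |
| 50% | 1.0 |

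The formula applies to any parameter in its own unit. Sodium is used only because its scale is familiar; it is the best covered of the labs by other tables.

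**7. Shift percentages.** The denominator is every subject with a baseline and any post-baseline result, whichever visit is shown. If 30% of them (assumed) have no Visit 7 result, the below, within and above percentages at Visit 7 sum to 100% − 30% = 70%, unless a missing category is shown. If EOS/ET is not a column, a subject whose only post-baseline value is at ET counts in the denominator and in no cell.

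**The case against.** The strongest reply is that these are ordinary observed-case tables. Each row describes those on study at that visit, no test or decision depends on it, and the safety signal is carried by tables that do take ET values. Section 6.2 also speaks only of the appropriate summaries, which does not oblige every table to hold every value. Most of this stands, and it rules out several stronger readings that a reader might infer:

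- *The shift tables also omit ET values.* The text does not say so. Lab shifts run to each visit without the Visit 3 to 7 limit, so the place of ET there is unclear, not excluded. No ECG shift table is planned.
- *ET values of parameters without PCS limits reach listings only.* The clinical-significance summary covers each lab parameter, and ECG abnormalities are counted by type. Neither is limited to Visits 3 to 7.
- *The tables describe only those who stayed.* A subject who leaves after Visit 5 still contributes at every lab or ECG visit attended up to then.
- *ET values are the leavers' worst values.* The documents do not say this, nor that ET values are on treatment.

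The reply does not tell the programmer where a year-1 ET value goes in the continuous tables. It also does not reconcile the Visit 3 to 7 limit with the wider wording of 5.3.2.

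**Conclusion.** The point holds for the continuous lab and ECG summaries in year 1. As written, 7.7.2 and 7.7.3 give ET values no row, nothing else in the SAP brings them in, and this does not match 5.3.2 and sits badly with 6.2. The loss is the numeric change at ET, and it matters most for parameters with no numeric category.

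The size cannot be known from the documents, which give neither a dropout rate nor leavers' values. The 0.2 to 1.0 mEq/L for sodium rests wholly on the assumed 2 mEq/L difference and 10% to 50% leaving. It compares a last-value mean with a Visit 7 observed mean, which are two different quantities. If leavers resemble stayers, it is zero. The effect is on the completeness of descriptive safety reporting, not on any inference. Because the data are collected anyway, the change is a cheap improvement worth making.

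**What to change.** In SAP 7.7.2 and 7.7.3, add two rows to the continuous tables of observed value and change from baseline: one for year-1 EOS/ET, and one for the last on-treatment value. State how on-treatment is defined, since an ET sample may be taken after the last dose.

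In 7.7.2, state that the lab shift table includes EOS/ET, and base each visit's percentages on subjects with a baseline value and a result at that visit.

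The cost is extra programming and one added definition. No new data are needed.

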**5. Seizure-free**

Subjects who did not have any seizure as per the seizure diary during that time period will be deemed seizure free, for the corresponding interval of interest. However, subjects who discontinue prior to Visit 7 will be considered not seizure-free for the interval when the discontinuation takes place and all subsequent intervals (even if the subjects are seizure-free at the time of discontinuation). That is, subjects must complete each interval of interest without any seizures to be considered seizure-free for each interval of interest.

The number and percent of seizure-free subjects will be presented for the interval of interest, for each interval the percent will be based out of the number of subjects in the ITT population entering each interval of interest.

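### SAP 7.7.2 gives by-visit laboratory shift percentages a denominator with no visit index; programmed as written, any subject untested at a visit lowers every category at that visit

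*SAP*

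**What the plan says.** Two consecutive sentences in SAP 7.7.2 (Clinical Laboratory Evaluation) define the shift tables. The first sets the unit of the table, which is the visit: "Shifts from baseline to each visit will be produced to show the percentage of subjects with laboratory test values below, within, and above". These three categories refer to the laboratory's reference limits. The second sentence sets the denominator: "The percentage will be based on the number of subjects with a baseline result and at least one post-baseline result for each parameter". That denominator varies by parameter and not by visit.

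The surrounding text bears on it as follows.

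- The companion summaries of values and change from baseline "will be displayed at each scheduled visit (i.e. Visit 3-Visit 7) for each continuous laboratory parameter".
- SAP 6.2 states: "No imputation is planned for any safety measures". It also says that dropouts are not replaced.
- SAP 6.1 promises counts and percentages for categorical variables. Neither it nor the laboratory text in 5.3.2 gives another denominator for the shifts.
- In the schedule (SAP 5.1), the row "Clinical Laboratory Evaluation (Serum Chemistry, Hematology, and Urinalysis" is marked at Visits 3 to 7 and at the end-of-study or early-termination visit. Note g reads: "These assessments are not required to be performed if this visit falls in the post-1-year part of the study". Early termination during year 1 is therefore a scheduled laboratory time point.
- The row "Bone Turnover Markers" has no entry at Visits 3 or 4.

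**The concern.** A requirement of any later result suits a single overall shift, such as a shift to the worst value after baseline. Attached to a table for each visit, it keeps in the denominator people who cannot appear in any cell. Someone tested at Month 1 who leaves before Month 6 still counts at Months 6, 9 and 12.

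Safety and tolerability are the primary objective (SAP 2.1), and a by-visit shift table is read for trend over time. If the denominator stays fixed while the number tested falls, loss of subjects is mixed into that trend. A stable abnormality rate would then seem to decline, and a modest rise could be hidden.

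**Working it through.** The documents give no figure to reproduce here, so the check is algebra followed by illustrations with assumed inputs.

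**Definitions, for one parameter and one visit v**

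- x_v: subjects in a given shift category at visit v
- n_v: subjects with results at both baseline and visit v
- N_any: subjects with a baseline result and any later result (the denominator in 7.7.2)
- f = n_v / N_any, which is at most 1

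**Step 1: the printed percentage.** With no imputation (6.2), only the n_v subjects can supply x_v. Hence

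x_v / N_any = (x_v / n_v) × (n_v / N_any) = (rate among those tested) × f.

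**Step 2: the column total.** Below, within and above together contain n_v subjects, so they total 100 × f percent. This is 100% only when f = 1.

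**Step 3: can f be below 1 in this study?** Yes. Laboratory tests fall at Months 1, 3, 6, 9 and 12 and at a year-1 early termination, and dropouts are not replaced. A subject who leaves before a given visit can have a later-than-baseline result and none at that visit.

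**Step 4: single-visit illustration.** Assumed rates among those tested are 10% above, 5% below and 85% within.

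| f (assumed) | Above | Below | Within | Total |
|---|---|---|---|---|
| 1.0 | 10.0% | 5.0% | 85.0% | 100% |
| 0.9 | 9.0% | 4.5% | 76.5% | 90% |
| 0.8 | 8.0% | 4.0% | 68.0% | 80% |
| 0.7 | 7.0% | 3.5% | 59.5% | 70% |
| 0.5 | 5.0% | 2.5% | 42.5% | 50% |

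The ratio of above to within is 10/85 = 0.118 in every row, because all cells shrink together. In counts (also assumed): with N_any = 200, 140 tested and 14 above, the table prints 14/200 = 7.0%, while the rate among those tested is 14/140 = 10.0%.

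**Step 5: trend illustration.** Assumed f and rates at Visits 3 to 7:

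| Visit | f | Constant 10% prints as | True rate if rising | Rising rate prints as |
|---|---|---|---|---|
| 3 | 0.97 | 9.7% | 10% | 9.7% |
| 4 | 0.90 | 9.0% | 11% | 9.9% |
| 5 | 0.80 | 8.0% | 12% | 9.6% |
| 6 | 0.72 | 7.2% | 13% | 9.4% |
| 7 | 0.65 | 6.5% | 14% | 9.1% |

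Under these inputs a steady rate appears to fall by about a third, and a rise of 4 percentage points prints as a slight decline.

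**The case against.** The best defence is that the sentence is loose wording, perhaps carried over from an overall shift, and that a programmer would use paired results at each visit anyway. That may happen, so the effect is conditional on literal programming. It does not remove the point: the sentence states a different rule, and nothing elsewhere in the SAP overrides it.

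Second, a reader could recover the proper rate. Counts accompany percentages, and the change-from-baseline summaries give the paired number at each visit for continuous parameters. Laboratory listings are planned, and columns that do not total 100% are a visible signal. This stands, and it limits the harm. Still, a percentage should not need correcting from another table.

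Third, a fixed denominator is not wrong in itself, and a per-visit denominator has its own weakness: it describes only subjects who remain and are tested, so it too can fall if those with abnormal values leave. This also stands. A fixed denominator would be sound with a missing category shown, but 7.7.2 does not specify one.

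Some stronger readings are tempting and not supported.

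- A reader might infer that the reported abnormality rates will certainly be understated. That needs both literal programming and subjects without a result at the visit. Where everyone in the denominator is tested, there is no dilution.
- A reader might extend the sentence to the summaries of potentially clinically significant values or to the sodium categories. The text does not tie it to either.
- A reader might cite the seizure-free rule in 5.2.2 ("for each interval the percent will be based out of the number of subjects in the ITT population entering each interval of interest") as the SAP's own precedent for a per-visit denominator. It is not one. Its denominator is subjects entering the interval, and those who discontinue are counted as not seizure-free, so unobserved subjects stay in.

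**Conclusion.** The point holds as a minor error in a stated rule. Applied literally, the denominator in 7.7.2 multiplies every by-visit shift percentage by the fraction of eligible subjects tested at that visit, and the categories total that fraction. Given literal programming, the distortion is never upward and is zero at a visit where all eligible subjects are tested.

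Its size in this trial cannot be stated, because the documents give no attrition or per-visit testing rates. Every rate and fraction in the tables above is an assumption. The safety analysis is descriptive, and no test or decision rule is attached to this table.

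**What to change.** Replace the denominator sentence in SAP 7.7.2 with:

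> At each visit at which the parameter is scheduled, the shift percentage will be based on subjects with a baseline result and a result at that visit; this number will be shown.

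The restriction to scheduled visits is needed because of parameters such as the bone markers, which are not due at Visits 3 or 4. Add a table note that the percentages describe subjects still in the study and tested at that visit.

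An acceptable alternative is to keep the fixed denominator and print a missing category at each visit, so that the column totals 100%.

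The cost of the first option is one sentence, a changed denominator in the shift-table program, one number per visit and a table note. Neither option needs new data or an additional table.

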**Table 2: PCS Criteria for Laboratory Parameters**

Parameter Name	PCS Low	PCS High
Hematology		
WBC	$\leq 2.8 \times 10^9/L$	$\geq 16 \times 10^9/L$
Neutrophils	$< 1.5 \times 10^9/L$	$> 13.5 \times 10^9/L$
Lymphocytes	N/A	$> 12 \times 10^9/L$
Monocytes	N/A	$> 2.5 \times 10^9/L$
Eosinophils	N/A	$> 1.6 \text{ k/mm}^3$
Basophils	N/A	$> 1.6 \text{ k/mm}^3$
Hemoglobin for Females	$\leq 9.5 \text{ g/dL}$	$\geq 17.5 \text{ g/dL}$
Hemoglobin for Males	$\leq 11.5 \text{ g/dL}$	$\geq 19.0 \text{ g/dL}$
Hematocrit for Females	$\leq 32\%$	$\geq 54\%$
Hematocrit for Males	$\leq 37\%$	$\geq 60\%$
RBC	$\leq 3.5 \times 10^{12}/L$	$\geq 6.4 \times 10^{12}/L$
Platelet Count	$\leq 75 \times 10^9/L$	$\geq 700 \times 10^9/L$
Chemistry		
Sodium	$\leq 126 \text{ mEq/L}$	$\geq 156 \text{ mEq/L}$
Potassium	$\leq 3 \text{ mEq/L}$	$\geq 6 \text{ mEq/L}$
Chloride	$\leq 90 \text{ mEq/L}$	$\geq 118 \text{ mEq/L}$
Calcium	$< 8.2 \text{ mg/dL}$	$\geq 12 \text{ mg/dL}$
AST	N/A	$\geq 3 \times \text{ULN}$
ALT	N/A	$\geq 3 \times \text{ULN}$
Alkaline phosphatase	N/A	$\geq 3 \times \text{ULN}$
Creatinine	N/A	$\geq 2 \text{ mg/dL}$
BUN	N/A	$\geq 30 \text{ mg/dL}$
Total bilirubin	N/A	$\geq 2 \text{ mg/dL}$
Total protein	$\leq 4.5 \text{ g/dL}$	$\geq 10 \text{ g/dL}$
Albumin	$\leq 2.5 \text{ g/dL}$	N/A
Glucose	$\leq 40 \text{ mg/dL}$	$\geq 175 \text{ mg/dL}$
Creatinine Phosphokinase	N/A	$> 2.5 \times \text{ULN}$

Phosphate	< 2.0 mg/dL	> 5.3 mg/dL
HDL-Cholesterol	< 30 mg/dL	N/A
LDL-Cholesterol	N/A	> 160 mg/dL
Total Cholesterol	> 300 mg/dL	N/A
Triglycerides	N/A	> 2.5 x ULN
Blood Coagulation		
aPTT	N/A	> 1.5 ULN
INR	N/A	> 1.5 ULN
Thyroid Function		
Free T3	< 0.20 ng/dL	> 0.415 ng/dL
Free T4	< 0.75 ng/dL	> 1.75 ng/dL

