### 12-Lead ECG

Observed values and change from baseline will be summarized for each visit, where change from baseline is the result of interest minus the baseline result (Visit 2 from protocol 093-045 or 093-046).

The number and percentage of subjects with QTc-F values in the following categories will be identified:

- QTc-F >500 ms at any postdose time point not present at baseline
- QTc-F >480 ms at any postdose time point not present at baseline
- QTc-F >450 ms at any postdose time point not present at baseline
- Change from baseline in QTc-F  $\geq$ 60 ms for at least 1 postdose measurement
- Change from baseline in QTc-F  $\geq$ 30 ms for at least 1 postdose measurement, but <60 ms for all postdose measurements.

This categorical analysis will be also performed for QTc-B.

The incidence of specific ECG abnormalities will also be identified for the following categories:

- Overall abnormalities
- Rhythm abnormalities
- Conduction abnormalities
- Morphology abnormalities
- Myocardial infarction
- Presence of ST Segment abnormalities
- Presence of T wave abnormalities
- Presence of U wave abnormalities

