### Vital Signs

Observed values and change from baseline will be summarized for each visit, where change from baseline is the result of interest minus the baseline result (Visit 2 from protocol 093-045 or 093-046).

In addition, subjects meeting the sponsor defined vital sign PCS criteria (Table 3) will be identified.

A vital sign value is considered PCS low if it is below the specified low limit and it decreases from baseline more than the specified decrease from baseline limit. A vital sign value is considered PCS high if it is higher than the specified high limit and it increases from baseline more than the specified increase from baseline limit.

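### The laboratory PCS summary ignores PCS status at parent-study Day 0, so its percentages can mix pre-existing with new abnormalities

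*SAP*

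**What the plan says.** SAP section 5.3.2 (Clinical Laboratory Evaluation) says that "sponsor defined-potentially clinically significant (PCS) laboratory results will be identified using the criteria in Table 2". Table 2 has a low and a high column of fixed limits or multiples of ULN, and no column for change from baseline. Section 7.7.2 then says "The number and percentage of subjects with PCS criteria will be summarized by overall", followed by age group, race, gender, number of baseline AEDs and individual baseline AEDs. Section 6.5 lists PCS laboratory parameters among the five outcomes for subgroup summary and adds no baseline condition.

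A laboratory baseline is defined: "change from baseline is the result of interest minus baseline value (Visit 2/Day 0 from protocol 093-045 or 093-046".

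Elsewhere the SAP uses baseline in categorical safety rules:
- QTc, section 7.7.3: "QTc-F >500 ms at any post-baseline time point not present at baseline". Section 5.3.2 has the same rule.
- Vital-sign PCS, section 5.3.2: besides passing the high limit, a value is PCS high only if "it increases from baseline more than the specified increase from baseline limit". The low side mirrors this.
- Sodium categories, sections 5.3.2 and 7.7.2: restricted to subjects whose baseline sodium was normal.

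**The concern.** Safety and tolerability form the primary objective (SAP section 2.1), and there is no control arm to show how often a Table 2 limit is passed without open-label treatment. A reader will tend to take a PCS percentage as something that arose on eslicarbazepine. Under the rule as written, a subject beyond the limit at parent Day 0 and again during the extension counts the same as a subject who crossed it for the first time.

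The subgroup tables are more exposed than the overall table. Baseline-AED subgroups are defined by drugs taken before study treatment (section 6.5). If one of those drugs is associated with a laboratory abnormality, that abnormality may already be present at Day 0 and would appear in the table as a subgroup difference on eslicarbazepine.

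The documents make baseline PCS values plausible for at least one parameter. Creatine phosphokinase above 2.5 x ULN is a Table 2 criterion. The protocol's Amendment 1 summary explains that the test was added as a marker of muscle breakdown from seizures, and subjects entered the programme with seizures that existing drugs did not control well.

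**Working it through.** **Step 1: what the text fixes and what it leaves open.** The documents state no figure on this point, so there is none to reproduce.

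| Rule | Post-baseline stated? | Baseline status used? | Denominator stated? |
|---|---|---|---|
| Lab PCS (5.3.2, Table 2, 7.7.2) | No | No | No |
| Lab shift tables (7.7.2) | Yes | Yes, on the normal range | Yes |
| Sodium categories (5.3.2, 7.7.2) | Yes | Yes, normal baseline only | Subjects with normal baseline |
| QTc limits (5.3.2, 7.7.3) | Yes | Yes, excluded if present at baseline | No |
| Vital-sign PCS (5.3.2, Table 3) | Implied by the change | Yes, change required | No |

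**Step 2: can the shift tables recover the split?** They classify values as below, within or above the normal range. Take one subject who is above normal but not PCS at Day 0 and becomes PCS high. Take another who is PCS high at both times. Both appear as high at baseline and high later, so the shift tables cannot separate new from old PCS values.

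**Step 3: size, on assumed inputs.** Let
- b = share of subjects PCS at Day 0 (assumed 1%, 5%, 10%);
- p = probability that such a subject is PCS again after baseline (assumed 50%, 80%);
- i = share newly PCS among those not PCS at Day 0 (assumed 2%, 5%).

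Reported proportion = b × p + (1 − b) × i. Share of counted subjects who were already PCS = b × p / reported proportion.

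| b | p | Reported if i = 2% | Already PCS | Reported if i = 5% | Already PCS |
|---|---|---|---|---|---|
| 1% | 50% | 2.48% | 20% | 5.45% | 9% |
| 1% | 80% | 2.78% | 29% | 5.75% | 14% |
| 5% | 50% | 4.40% | 57% | 7.25% | 34% |
| 5% | 80% | 5.90% | 68% | 8.75% | 46% |
| 10% | 50% | 6.80% | 74% | 9.50% | 53% |
| 10% | 80% | 9.80% | 82% | 12.50% | 64% |

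One line in full, with b = 5%, p = 80%, i = 2%: 0.05 × 0.80 + 0.95 × 0.02 = 0.040 + 0.019 = 5.9%. With the 348 subjects named in the protocol's Amendment 3 summary, used only for scale, that is about 20 of 348. The new-onset figure is about 7 of 331 (2.0%).

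The ratio of reported to new-onset percentage runs from 5.45/5.0 = 1.09 to 9.8/2.0 = 4.9.

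**Step 4: subgroups.** Give two subgroups the same new onset (2%) and the same persistence (80%), but baseline prevalence of 2% and 10%:
- 0.02 × 0.80 + 0.98 × 0.02 = 3.56%
- 0.10 × 0.80 + 0.90 × 0.02 = 9.80%

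The table would show a 2.75-fold difference where new onset does not differ.

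**The case against.** The SAP is silent rather than wrong. It never says that subjects PCS at baseline are to be counted with new cases, and a programmer may apply a post-baseline rule by habit. Neighbouring sentences in section 7.7.2 speak of post-baseline or post-dose values, so counting someone on a Day 0 value alone would be a strained reading. That stands, and it makes the missing post-baseline condition the smaller part of the point. It does not settle how to treat a subject who is PCS at both times, or which denominator applies.

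A reader might infer that laboratory PCS is the only categorical safety result that ignores baseline. The documents do not support this. ECG rhythm, conduction, morphology and wave abnormalities (5.3.2, 7.7.3) and orthostatic effects (5.3.2, 7.7.5) are also counted without a baseline exclusion, and the laboratory section does have a baseline-restricted sodium analysis.

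A reader might also take the PCS percentage as the main categorical laboratory result. The SAP gives no such ranking. It also plans shift tables, sodium categories, a clinical-significance summary, a listing of AST/ALT elevations and a listing of PCS subjects. With the full laboratory listing, any PCS subject's baseline value can be looked up. This limits the harm but leaves the tabulated percentages unchanged.

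The analyses are descriptive, so no planned test is biased. Counting every on-treatment PCS value is also a defensible, conservative choice, because dropping subjects who were PCS at Day 0 would hide those who then worsen. This last objection is sound, and it shapes the fix.

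**Conclusion.** The point holds as a gap in specification. As written, the overall and subgroup laboratory PCS percentages can mix abnormality present at parent Day 0 with abnormality arising later, and no planned table separates the two at the PCS limits.

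The documents cannot give the size. Under the assumed ranges the table reports 2.5-12.5% against 2-5% new onset, and 9-82% of those counted were already PCS. At the low end (5.45% against 5.0%) the effect is trivial. It could be small for parameters with extreme limits and larger where baseline values near the limit are common. The two percentages answer different questions, and the difficulty is that the plan does not say which one it reports.

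A reader might infer something worse, such as 0.10 + 0.90 × 0.05 = 14.5% against 5%. That needs 10% baseline prevalence and full persistence, or counting of baseline-only values. Nothing in the documents establishes any of these, so it should not be quoted as the expected effect.

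**What to change.** In sections 5.3.2 and 7.7.2, define the laboratory PCS count as values after the first open-label dose that meet Table 2. Present it by PCS status at parent Day 0, separately for PCS low and PCS high, so that a low baseline does not remove a new high value:

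1. **Newly PCS.** The denominator is subjects who were not PCS in that direction at Day 0 and have one or more post-dose values.
2. **Already PCS at baseline.** Use a separate row, or a shift table on the PCS limits, so that subjects who worsen from a PCS baseline stay visible.

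Use the same layout in the subgroup tables, and keep the existing listing of PCS subjects. State how subjects without a Day 0 value are shown.

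No new data are needed, because Day 0 is already the laboratory baseline. The cost is one derived flag and one extra row per parameter. The headline PCS counts will be smaller than under a count of all on-treatment values, and a footnote should say why.
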